13 ASSESSMENT OF SAFETY

13.1 Adverse Events and Serious Adverse Events

13.1.1 Definition of Adverse Events (AE)

An adverse event is the development of any untoward medical occurrence or the deterioration of a pre-existing medical condition following or during exposure to a pharmaceutical product, whether or not considered causally related to the product. An undesirable medical condition can be symptoms (e.g., nausea, chest pain), signs (e.g., tachycardia, enlarged liver) or the abnormal results of an investigation (e.g., laboratory findings, electrocardiogram). In clinical studies, an AE can include an undesirable medical condition occurring at any time, even if no study treatment has been administered.

13.1.2 Definition of Serious Adverse Event (SAE)

An SAE is any untoward medical occurrence that results in any of the following outcomes:

• results in death;

- is life-threatening (defined as an event in which the participant was at risk of death at the time of the event; it does not refer to an event which hypothetically might have caused death if it were more severe);
- requires inpatient hospitalization or causes prolongation of existing hospitalization;
- results in persistent or significant disability/incapacity;
- is a congenital anomaly/birth defect;
- is an important medical event (defined as a medical event(s) that may not be immediately life-threatening or result in death or hospitalization but, based upon appropriate medical and scientific judgment, may jeopardize the subject or may require intervention [e.g., medical, surgical] to prevent one of the other serious outcomes listed above

13.1.3 Classification of an Adverse Event

13.1.3.1 SEVERITY OF EVENT

The severity of AEs and SAEs will be reported using the grading system outlined in the NCI Common Terminology Criteria for Adverse Events Version 5.0 (CTCAE). The CTCAE provides a grading (severity) scale for each AE term and AEs are listed alphabetically within categories based on anatomy or pathophysiology. The CTCAE (v5.0) displays Grades 1-5 with unique clinical descriptions of severity for each AE based on this general guidance:

CTCAE Severity Grading Summary			
Grade 1: Mild AE			
Grade 2: Moderate AE			
Grade 3: Severe or Disabling AE			
Grade 4: Life-Threatening AE			
Grade 5: Death related to AE			

The complete definitions of these grades are:

- Grade 1: Mild; asymptomatic or mild symptoms; clinical or diagnostic observations only; intervention not indicated.
- Grade 2: Moderate; minimal, local or noninvasive intervention indicated; limiting ageappropriate instrumental activities of daily living (preparing meals, shopping for groceries or clothes, using the telephone, managing money, etc.).
- Grade 3: Severe or medically significant but not immediately life-threatening; hospitalization or prolongation of hospitalization indicated; disabling; limiting self-care activities of daily living (bathing, dressing and undressing, feeding self, using the toilet, taking medications, and not bedridden).
- Grade 4: Life-threatening consequences; urgent intervention indicated.
- Grade 5: Death related to AE.

13.1.3.2 RELATIONSHIP TO STUDY AGENT

The relationship of each reported event to the study agent will be assessed and documented by a study investigator. An algorithm to help determine relatedness can be found in the Manual of Operations and Procedures (MOP).

13.1.3.3 EXPECTEDNESS

The Independent Medical Monitor (IMM) will be responsible for determining whether an SAE is **expected** or **unexpected**. An SAE will be considered unexpected if the nature, severity, or frequency of the event is not consistent with the risk information previously described for the study agent.

13.1.4 Time Period and Frequency for Event Assessment and Follow-up

Site personnel will regularly assess and report all reportable events occurring from the time a subject has signed and dated the informed consent form until the subject has completed their final evaluation. All events will be captured on the appropriate CRF and entered into WebDCUTM. Information to be collected includes event description, time of onset, PI's assessment of severity, seriousness, relationship to study agent (assessed only by those with the training and authority to make a diagnosis), time of resolution/stabilization of the event, a description of the event, relevant history, and concomitant medications/procedures. All reportable events will be followed for outcome information until resolution or until the last day of study participation. The information in WebDCUTM will be updated as more information becomes available.

13.1.5 Adverse Event Reporting

Site investigators or their designees must report adverse events meeting the following criteria in WebDCU[™].

- 1) Any serious adverse event
- Any non-serious adverse event that is possibly or definitely related to occurring with the study antithrombotic medications, risk factor management, or any brain or vascular imaging study
- 3) Primary or secondary endpoints (parenchymal intracerebral brain hemorrhage (ICH), ischemic stroke, vascular death, myocardial infarction, or any non-ICH major hemorrhage)
- Adverse events of special interest (asymptomatic or incidental cerebral infarct, TIA, ruptured aortic aneurysm, pulmonary embolus, acute ischemia of a limb or internal organ, overdose of study drug, and study drug exposure during pregnancy (occurring in subject or female partner of a male subject))

Non-serious adverse events meeting these criteria must be reported within 5 working days of site awareness and serious adverse events meeting these criteria within 24 hours, excluding weekends/holidays, of site awareness.

13.2 Other Reportable Events

Follow-up information regarding the course of pregnancy, including perinatal and neonatal outcome and, where applicable, offspring information must be reported in WebDCU[™] on Form 104: Adverse Event. Any pregnancy that occurs in a female partner of a male subject must also be reported. In order for the study team to collect any pregnancy information from the female partner, the female partner must sign an informed consent form for disclosure of this information.

Any study antithrombotic product quality complaints must be reported (via telephone or email) within 5 working days of site awareness to the CCC Project Manager or CCC Administrator. Examples include, but are not limited to:

- Mislabeling or misbranding
- Information concerning microbial contamination, including a suspected transmission of any infectious agent by a product

- Any significant chemical, physical, or other changes that indicate deterioration in the distributed product
- Any foreign matter reported to be in the product
- Physical defect (e.g., abnormal product odor, broken or crushed tablets, etc.)

This study is being conducted as an investigator-initiated, NINDS-funded protocol. The FDA has granted a waiver for an investigational new drug (IND) application. Thus, no formal safety reporting to the FDA will be done.

13.3 Unanticipated Problems and Unanticipated Events

13.3.1 Definition of Unanticipated Problems (UP)

The Office for Human Research Protections (OHRP) considers *unanticipated problems* (UPs) involving risks to participants or others to include, in general, any incident, experience, or outcome that meets **all** of the following criteria:

- Unexpected in terms of nature, severity, or frequency given (a) the research procedures that are described in the protocol-related documents, such as the REB-approved research protocol and informed consent document; and (b) the characteristics of the participant population being studied;
- Related or possibly related to participation in the research ("possibly related" means there is a reasonable possibility that the incident, experience, or outcome may have been caused by the procedures involved in the research); and
- Suggests that the research places participants or others at a greater risk of harm (including physical, psychological, economic, or social harm) than was previously known or recognized.

Examples of UPs include:

- Suspected abuse/misuse of study drug
- Inadvertent or accidental exposure to study drug
- More frequent or severe side effects than were anticipated as described in the protocol and consent form
- Malfunctioning of research equipment that results or could result in risk to subjects or others
- Interim findings (data analysis and/or safety reports) and/or data safety monitoring reports that indicate an unexpected change to the risks or potential benefits of the research, in terms of severity or frequency
- Publications in the literature that indicate new risks
- Changes in product labeling indicating new risks
- Incorrect labeling, dosing, or dispensing of study drug even if there is no indication of harm (e.g. randomization error)

Unanticipated events include UPs, but may also include other events that do not rise to the level of UPs as outlined above. These include protocol deviations or other unexpected problems that do not necessarily pose a safety concern.

13.3.2 Unanticipated Event Reporting

Clinical sites will report unanticipated events, including UPs and protocol deviations, in accordance with the guidelines listed in the MOP.

13.4 Study Oversight

Safety oversight will be under the direction of the NIH StrokeNet DSMB, which is composed of individuals with the appropriate expertise in overseeing stroke clinical trials. The DSMB will meet at least semiannually to assess safety data on each arm of the study. The DSMB will review data quality and completeness, monitor fidelity to the study protocol, review the adequacy of participant recruitment and retention, review SAEs, and AEs of special interest and make recommendations to the NINDS and the study co-PIs concerning trial continuation, modification, or conclusion.

Additionally, the DSMB may recommend modifications to the protocol if a reversible safety issue is identified. After each meeting, the liaison to the DSMB will prepare a letter to the study principal investigators, which will summarize the DSMB recommendations following the safety review. This letter will be provided to the CIRB and local REBs, where appliable, and site investigators.

The Independent Medical Monitor (IMM) will conduct a review of each SAE to determine expectedness. If the IMM adjudicates the event to be serious, unexpected, and study related, the event will be reported to the cIRB and other IRB/REBs with study oversight according to cIRB and local regulations via a Safety Report generated in WebDCU[™].

13.5 Study Halting Rules

The IMM is responsible for ongoing monitoring of reports of SAEs by the clinical centers within 72 hours to ensure Good Clinical Practices (GCP) and to identify safety concerns quickly. The IMM may suggest protocol modifications to the DSMB to prevent the occurrence of particular SAEs, such as modifying the protocol to require frequent measurement of laboratory values predictive of the event or to improve expeditious identification of SAEs. The NDMC will prepare regular reports concerning SAEs and submit them to the DSMB. In the event of unexpected SAEs or an unduly high rate of SAEs, the IMM will promptly contact the NINDS DSMB liaison, who will notify the DSMB Chair. The DSMB will convene an ad hoc meeting by teleconference or in writing as soon as possible. The DSMB will provide recommendations for continuing or halting the study to the NIH and the study co-PIs.

14 SAMPLE SIZE AND STATISTICAL ANALYSIS

Sample Size Determination for the Primary Safety Outcome

The safety analysis is prespecified to occur when the first 450 randomized subjects have completed the 1-year follow-up period, resulting in approximately 150 patient-years of follow-up in each arm. While the 450th subject is completing the 1-year follow-up period, enrollment projections (15 subjects per arm per month) suggest that an additional 180 subjects per arm will have been randomized. The follow-up time available for these additional subjects will vary but is expected to be approximately 6 months on average, for an additional 90 patient-years of follow-up (180*6/12) per arm. The safety analysis will use available data on all enrolled subjects and is therefore expected to include approximately 240 patient-years of follow-up per arm.

Within each treatment arm, an analysis will be conducted to evaluate an excess risk of ICH as well as non-ICH major hemorrhage. In SAMMPRIS, the ICH rate was 0.5 (exact 80% CI 0.05 - 1.9), and the non-ICH major hemorrhage rate was 2.4 (exact 80% CI 1.2 - 4.5), per 100 patient-years on clopidogrel + aspirin. Even though clopidogrel was only used for 90 days in SAMMPRIS

and will be used for 1 year in CAPTIVA, we are using the 80% CI of the SAMMPRIS rates to be conservative and not overestimate the hemorrhage rates on clopidogrel + aspirin. In each experimental arm, the hypothesis for the safety analysis is that the rate is greater than these upper 80% confidence limits derived from SAMMPRIS. This hypothesis will be tested with a one-sided 0.05 level of significance because we are only interested in identifying an increase in risk (not a decrease). If an experimental arm crosses this safety boundary, this will initiate an unplanned, for cause, futility analysis in order to weigh the risk:benefit ratio of the corresponding experimental arm. With 240 patient-years of follow-up, the safety analysis has 80% power to reject the stated null hypothesis for the true event rates shown in **Table 3**.

Table 3. Safety Analysis			
Safety Event	Null Hypothesis (per 100 patient-years)		
ICH	Rate ≤1.9		
Non-ICH major hemorrhage	Rate ≤4.5		

Sample Size Determination for the Primary Efficacy Outcome

All subjects will be followed for one year for the primary outcome. The sample size was calculated based on a two-sample survival analysis comparing the time-to-event of a single experimental arm to clopidogrel + aspirin in EAST v6. The assumed event rate in CAPTIVA is based on high-risk subjects in the medical arm of SAMMPRIS who presented with a symptomatic infarct. The 1-year rate of ischemic stroke, ICH or vascular death was 27%.^{6,7} On the other hand, combining clopidogrel and aspirin for 1 year is likely to lower the rate of the primary endpoint so we have assumed a 24% primary event rate in the clopidogrel + aspirin arm. We are seeking a hazard ratio (HR) of 0.66 in CAPTIVA as the reduction in the rate of primary endpoint that would be required to overcome the anticipated higher risk of bleeding in the rivaroxaban and ticagrelor arms and the higher cost of these medications. The PRINCE trial demonstrated a HR of 0.45 for stroke in the ticagrelor + aspirin arm compared with the clopidogrel + arm in participants with large artery atherosclerosis,³⁰ and the COMPASS trial demonstrated a HR of 0.33 for ischemic stroke in the low dose rivaroxaban + aspirin arm compared to aspirin alone in subjects with a previous ischemic stroke.³⁸ Thus a HR of 0.66 also seems like an achievable target in CAPTIVA from ticagrelor + aspirin or low dose rivaroxaban + aspirin versus clopidogrel + aspirin.

For the comparison of a single experimental arm to clopidogrel + aspirin, the sample size was calculated for a two-sample survival analysis using EAST v6. In order to detect a HR of 0.66 (decrease in events from 24% to 16.56%) with 80% power, using a two-sided 0.05 level of significance, the required sample size per comparison is 948 (474 per arm). This calculation includes inflation for an interim futility analysis, conducted according to an O'Brien-Fleming error spending function after 50% of events have occurred. The calculation also includes inflation to account for approximately 5% dropout, assuming that dropout is a competing risk. In SAMMPRIS, 3% in the medical arm were lost over the first year of follow-up, so our 5% drop out estimate at 12 months is reasonable. An additional inflation factor of ~1.18 is then applied to account for dilution of the treatment effect associated with approximately 8% non-compliance with antithrombotic therapy, yielding a sample size per comparison of 1122 subjects (561 per arm). The inflation factor is derived via $1/(1-R^2)$, where R represents the non-compliance rate, as suggested in Friedman, Furberg, and DeMets.⁷⁸ We expect the non-compliance will largely result from adverse events from the antithrombotic medications (major hemorrhages in all 3 arms and dyspnea in the ticagrelor arm) but we do not expect these rates will exceed 8% in 1 year of followup in any arm of the trial. We expect treatment crossover to be very low because it is unlikely that subjects who do not have a primary endpoint will be switched from their blinded treatment arm to

open label treatment with one of the antithrombotic treatments being evaluated in CAPTIVA (note that rivaroxaban and ticagrelor are currently not approved for sICAS). We also expect that it will be very uncommon that subjects will undergo stenting or angioplasty or surgical bypass for their sICAS without having a stroke, which would be a primary endpoint. If a participant does undergo one of these procedures without having a primary endpoint, he/she will continue to be followed in the trial according to intention to treat. Because the same clopidogrel + aspirin arm is used as the control in both comparisons, an additional 561 subjects are required. This results in a total sample size of 1683 subjects. The main intent of CAPTIVA is to establish whether either of the two novel therapies is more effective than the current standard of care for sICAS. These experimental arms are evaluated in a single trial only to improve efficiency. The hypotheses do not constitute a family of hypotheses which must be interpreted together to support a single efficacy declaration; instead, the comparison of each experimental arm to the standard of care arm can be interpreted independently of the other. i.e., the chance of a false positive outcome for either claim of effectiveness is not increased by the presence of the other hypothesis. As such, a multiplicity adjustment is not required.⁷⁹⁻⁸¹

Sample Size Re-Estimation

To reduce the likelihood of an underpowered study due to incorrect assumptions, we propose to conduct a blinded sample size re-estimation in stage 2 prior to the planned interim futility analysis. This sample size re-estimation will occur approximately three months prior to the planned interim futility analysis. Refer to the separate Statistical Analysis Plan for more details on the sample size re-estimation.

The results of the sample size re-estimation will only be shared with the DSMB in closed session. This is done in order to maintain the study blind and avoid potential investigator bias. Ultimately it is the DSMB's decision to recommend an increase in the total sample size, and this decision should take into account the study conduct as well as the safety profile. Administratively, the unblinded statistician will provide the information to the DSMB. This will include the impact on estimated sample size if the power were to be maintained at 80% or reduced. This notification will include a brief report of the safety data (adverse event information by treatment arm) and data quality (protocol deviations by treatment arm). If the inclusion of additional subjects is recommended to maintain adequate power, the DSMB may recommend postponing the planned interim futility analysis (scheduled to occur 3 months after the sample size re-estimation) until a decision about an increase in sample size has been made by NINDS.

Planned Interim Analysis for Futility

One planned Interim analysis for overwhelming futility, conducted according to the beta-spending approach using O'Brien-Fleming type stopping boundaries, is pre-specified to occur when 50% of primary endpoints have been reported. The threshold to reject the null hypotheses for overwhelming futility of a given comparison are provided in the table below.

Analysis Look #		Approximate Number of Events	p-value to Stop Experimental Arm	
Interim	1	94	p>0.719	
Final	2	187	p > 0.05	

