4 SUMMARY OF STUDY DESIGN AND ORGANIZATION

Overview of the CAPTIVA Trial. CAPTIVA is a 3-arm, double-blind Phase III trial. Subjects with a symptomatic infarct attributed to 70-99% stenosis of a major intracranial artery (middle cerebral, intracranial carotid, intracranial vertebral, or basilar) will be randomized to 1-year treatment with:

- 1) ticagrelor (180 mg loading dose*, then 90 mg twice daily), or
- 2) low dose rivaroxaban (2.5 mg twice daily), or
- 3) clopidogrel (600 mg loading dose*, then 75 mg daily).

*Refer to Section 10.1 for exceptions to loading dose administration for study subjects

All subjects will also be treated with aspirin (81 mg daily) and receive intensive risk factor management according to the SAMMPRIS protocol.⁵⁹ Subjects will be evaluated at 1 month, 4 months, 8 months, and 1 year after randomization. A mouthwash or buccal swab sample will be sent to the University of Florida Center for Pharmacogenomics and Precision Medicine Genotyping Core Laboratory where it will be stored for *CYP2C19* genotype analysis. Since the *CYP2C19* genotype results do not affect randomization or treatment during the study, the genotype analysis will only be performed after randomization and the results will remain blinded to the investigators and subjects until the end of the trial.

The trial is designed to compare the efficacy of the experimental arms to the clopidogrel arm. A prespecified interim safety analysis concludes the first stage of CAPTIVA and will identify an increased risk of the primary safety endpoints of parenchymal ICH or non-ICH major hemorrhage in the low dose rivaroxaban and ticagrelor arms. If a safety concern is identified in an experimental arm at the time of the pre-specified interim safety analysis, an early futility analysis will determine

whether that arm progresses to the second stage of the trial. During the second stage of the trial, a planned interim futility analysis will be performed when 50% of the expected number of primary endpoints have occurred. At the conclusion of the trial, efficacy of the remaining arms will be evaluated. A schematic of the trial design is shown in **Figure 1**.

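### The interim futility threshold (stop if p>0.719) has no direction; applied as printed on the design's two-sided scale, it does not stop arms observed clearly worse than clopidogrel

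*Protocol*

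**What the plan says.** Protocol Section 14 (Planned Interim Analysis for Futility) plans one look for overwhelming futility, "conducted according to the beta-spending approach using O'Brien-Fleming type stopping boundaries", at half of the primary endpoints. The table column is headed "p-value to Stop Experimental Arm". It has two rows: p>0.719 at about 94 events (interim) and p≥0.05 at about 187 events (final). The lead-in is "The threshold to reject the null hypotheses for overwhelming futility of a given comparison are provided in the table below". Each experimental arm is compared with clopidogrel separately, once that comparison reaches its event count.

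The only sidedness stated for the efficacy comparison is in the sample size text of the same section: "using a two-sided 0.05 level of significance". The design goal to which it applies reads "In order to detect a HR of 0.66 (decrease in events from 24% to 16.56%) with 80% power". The aim in Section 3 is directional, namely superiority over clopidogrel in lowering the 1-year event rate. The note to Figure 1 in Section 4 refers to SAP Section 8.4 for more detail on the futility look. The SAP was not available for this check.

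**The concern.** A futility rule should stop the arms least likely to show superiority. A two-sided p-value is large only near the null. It becomes small again as an arm looks worse than control, exactly as it does when an arm looks better. Without a sign, a rule of the form p greater than a cut therefore stops an arm close to HR 1 and passes an arm well above it.

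This look is the only quantified interim test of the primary endpoint in the protocol. If the row is applied literally, an arm with more strokes, intracerebral hemorrhages or vascular deaths than clopidogrel, and almost no chance of final success, counts as not futile and continues to recruit.

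**Working it through.** **Inputs (Protocol Section 14).** Two-sided alpha 0.05; 80% power; HR 0.66; 1-year rates 24% and 16.56%; 948 subjects per comparison (474 per arm) before the non-compliance inflation, with "inflation to account for approximately 5% dropout, assuming that dropout is a competing risk"; looks at 94 and 187 events; O'Brien-Fleming type beta spending.

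**1. Reproduce the event count.** Expected events are 474 × (0.24 + 0.1656) × 0.975 = 187.4, where 0.975 assumes that 5% dropout costs about half a year each. A design without an interim look needs 4(1.960 + 0.842)²/(ln 0.66)² = 182 events, so 187 includes a small inflation for the futility look.

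**2. Reproduce the threshold.** Take a symmetric futility region |Z|<b with spending β(t) = 4 − 4Φ(z₀.₉₅/√t), final critical value 1.96 and total type II error 0.20.
- β is 0.0400 at t = 0.50 and 0.0407 at t = 94/187.
- The required drift is 2.838, so events = 4 × 2.838²/0.4155² = 186.6, against 187 printed.
- b = 0.354 (two-sided p = 0.724) at t = 0.50 and b = 0.362 (p = 0.717) at t = 94/187. The printed 0.719 lies between them.

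**3. Alternatives tried.**
- One-directional O'Brien-Fleming beta spending gives 187 events (binding) or 191 (non-binding), but a boundary of one-sided p 0.29–0.30, or two-sided p 0.57–0.59.
- A one-sided p of 0.719 means Z = −0.58 and spends only 0.5% of beta. It matches no O'Brien-Fleming variant tried.
- A one-directional boundary with quadratic spending (0.20t²), which is not O'Brien-Fleming, gives 187.1 events and two-sided p 0.715 at t = 0.50 (0.707 at 94/187). A cut near 0.36 can thus also arise from a directional design. The symmetric region is the best fit to the stated method, not a proof of intent.

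**4. Translate to an HR.** With 1:1 allocation, Z = −ln(HR) × √94/2. Two-sided p>0.719 is |Z|<0.360, so the stopping band is HR = exp(±2 × 0.360/√94) = exp(±0.0742), or 0.928 to 1.077. Conditional power for the remaining 93 events, assuming HR 0.66 from then on, is 1 − Φ([1.96√187 − Z√94 − 93 × 0.4155/2]/√93).

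| Observed HR at 94 events | Two-sided p | Meets p>0.719? | Conditional power |
|---|---|---|---|
| 1.1 | 0.64 | no | 11% |
| 1.2 | 0.38 | no | 5% |
| 1.3 | 0.20 | no | 2% |
| 1.5 | 0.049 | no | 0.3% |

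**5. Probability of stopping.** With m = −ln(true HR) × √94/2, the rule as written stops with probability Φ(0.36 − m) − Φ(−0.36 − m). The signed rule stops with probability Φ(0.36 − m).

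| True HR | As written | Signed, same cut |
|---|---|---|
| 1.0 | 28% | 64% |
| 1.2 | 19% | 89% |
| 1.3 | 13% | 95% |
| 1.5 | 4% | 99% |

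**6. Power at HR 0.66 with 187 events.** This is P(not stopped at the look and final Z>1.96), with means 2.014 and 2.841 and correlation √(94/187). The undirected rule gives 80.1% and the signed rule at 0.36 gives 80.0%.

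**The case against.** **Sidedness is not printed, and detail is deferred to the SAP.** Both are true. The two-sided reading is an inference, and SAP Section 8.4 may supply a sign. But the protocol prints an operative threshold, not merely a pointer, and the printed row supports incompatible decisions. At an observed HR of 1.0 the undirected reading stops, while a one-sided p of 0.719 (HR above 1.127) continues. At 1.2 the two are reversed. A direction in the SAP would not correct the protocol row.

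**The DSMB would not let a harmful arm run.** It reviews safety by arm at least semiannually, monitors hemorrhage throughout, and can be convened ad hoc for an unduly high rate of serious adverse events (Sections 4.1, 13.4, 13.5). That safeguard stands, and a reader should not infer that this row is the only protection. It is separate, however, and sets no boundary on the primary endpoint.

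**A signed rule is more aggressive than overwhelming futility suggests.** This stands in part. Null arms would stop 64% of the time instead of 28%, which is a design choice for the sponsor to accept knowingly.

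**A wider reach.** A reader might infer that the same scale governs the analysis triggered by a bleeding signal, which Section 4 says ("an early futility analysis will determine") decides whether an arm progresses. No section gives that analysis a p-value threshold, and Section 14 describes it as weighing risk against benefit. The documents do not support the extension.

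**Conclusion.** The point holds for the printed interim row. On the two-sided scale that best fits the stated design, the rule stops only arms with an observed HR of about 0.93 to 1.08. Arms observed worse than about 1.08 do not meet it, and the probability of stopping falls as the true effect worsens.

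A reader might infer that every arm doing worse than clopidogrel continues. That is too strong, because arms observed between 1.00 and about 1.08 do stop. The final superiority test and its type I error are not affected.

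The figures assume a log-rank or Cox Z with 1:1 allocation, exactly 94 and 187 events, and a two-sided p. If p were one-sided for benefit, the rule would be directional and the defect would disappear, but the threshold would no longer match the stated O'Brien-Fleming beta spending.

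**What to change.** Restate the interim row as a directional rule on the same cut. With Z signed so that positive means fewer events on the experimental arm, stop that arm if Z<0.36. The row can equally say one-sided p for benefit above 0.36, or observed HR above about 0.93 at 94 events, with a statement that every HR above 1 is included. Align SAP Section 8.4 with the same sign convention and scale.

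No added subjects are needed, and power at HR 0.66 with 187 events is 80.0% against 80.1%. The cost is the higher stopping rate for a truly null arm (64% against 28%), which the sponsor should confirm is acceptable.

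Keeping the 0.36 cut is deliberate. Re-deriving the boundary with one-sided O'Brien-Fleming beta spending would move it to about Z = 0.54. That lowers power at 187 events to 79.2%, a loss of about 0.9 percentage point, and stops a null arm about 70% of the time. It is not needed to correct the direction.
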